5.3.2.2. Supplementary Estimand (Estimand 2)

In this supplementary estimand, all intercurrent events are addressed by the **composite strategy**. The components of the supplementary estimand and variable (endpoint) are the same as those for the primary estimand.

Under Estimand 2, participants who have intercurrent events ICE 1-3 prior to the Week 16 will have non-response for the primary endpoint response, regardless of the observed data.

5.3.3. Analysis Methods

The primary endpoint will be analyzed at Week 16 DBL based on the primary estimand. If a participant experiences ICE of 1 or 2 prior to Week 16, will be treated as non-responders for, IGA score of cleared (0) or minimal (1) response, for the primary analysis. If a participant experiences ICE of 3 then observed value will be used if available.

This primary analysis will include all data collected up to and including Week 16 for all participants in the primary efficacy analysis set. In these primary efficacy analyses, data from all randomized participants will be analyzed according to their assigned treatment group. The primary endpoint at Week 16 will be summarized for each treatment group.

To address the primary objective, a 2-sided ($\alpha=0.05$) CMH chi-squared test stratified by special site (scalp, face, intertriginous, genital) will be used for the primary endpoint.

Statistical analysis for both primary (Estimand 1) and supplementary estimand (Estimand 2) are the same.

The overall Type I error rate will be controlled at the significance level of 0.05. The study will be considered positive if the guselkumab group is significantly different from the placebo. Primary endpoint will be tested at a 2-sided α -level of 0.05.

If the comparison is positive for the primary endpoint, the testing will continue to the major secondary endpoint.

Participants with ICE categories of 1 or 2 before Week 16 will be considered as non-responders at Week 16. Participants with ICE category of 3 before Week 16, observed data will be utilized in the analysis. After accounting for the ICEs for the primary estimand, participants with the missing data of the primary endpoint at Week 16 will be considered as non-responders.

5.3.4. Subgroup Analyses

The consistency of treatment effect, the primary endpoint will be evaluated for the subgroups defined in Section 5.7.8, using the primary estimand (**Estimand 1**). For each subgroup analysis, the analysis set is the individual subgroup (Section 5.7.8) of the primary efficacy analysis set.

- For each of the subgroups, the difference between the guselkumab treatment group and placebo group in the proportion of participants achieving IGA score of cleared (0) or

minimal (1) at Week 16 and its 95% confidence interval (when the numbers of participants permit) will be calculated.

In addition, the primary endpoint at Week 16 by region, country and investigator site will be summarized.

5.3.5. Summary of Analyses Related to the Primary Endpoint

Table 7 below provides an overview of the analyses related to the primary endpoints, the estimands, the analysis sets, the data handling rules to be used, and the analysis methods and summary statistics.

Table 7: Summary of Analyses Related to the Primary Endpoint at Week 16

Analysis (Analysis Set)	Missing data	Analysis method/Summary statistics
Analyses based on Primary Estimand (Estimand 1) , where ICEs 1-2 are handled by the composite strategy , and ICE 3 is handled by the treatment policy strategy		
Full Analysis Set (FAS)	Missing data due to missed visits or missed data collection. Participants with missing data are considered to be non-responders' imputation (NRI)	
 Summaries of the proportion of participants who achieved the endpoint Treatment difference (guselkumab group-placebo group) and 95% CI P-values based on CMH chi-squared test stratified by special site and represent the comparison with placebo.
Subgroup Analyses (Individual subgroup levels defined in Section 5.7.8, Full Analysis Set (FAS))	Missing data due to missed visits or missed data collection. Participants with missing data are considered to be non-responders' imputation (NRI)	
 Summaries of the proportion of participants who achieved the endpoint by subgroup Treatment difference (guselkumab group-placebo group) and 95% CI P-values based on CMH chi-squared test stratified by special site and represent the comparison with placebo.
Analyses based on Supplementary Estimand (Estimand 2) , where all the intercurrent events are addressed by the composite strategy in which non-responder is used after the occurrence of an ICE.		
Supplementary Analysis 1 (Full Analysis Set (FAS))	Missing data due to missed visits or missed data collection. Participants with missing data are considered to be non-responders' imputation (NRI)	
 Summaries of the proportion of participants who achieved the endpoint Treatment difference (guselkumab group-placebo group) and 95% CI P-values based on CMH chi-squared test stratified by special site and represent the comparison with placebo.

5.4. Secondary Endpoint(s) Analysis

5.4.1. Major Secondary Endpoint(s)

There are 12 major secondary endpoints for this study and listed below:

To evaluate the additional efficacy of guselkumab vs placebo

1. Change from baseline in BSA affected at Week 16
2. Change from baseline in total Psoriasis Area Severity Index (PASI) score at Week 16
3. The proportion of participants who achieve an IGA score of cleared (0) at Week 16
4. The proportion of participants who achieve a PASI 90 response at Week 16
5. The proportion of participants who achieve a PASI 100 response at Week 16
6. The proportion of participants who achieve a scalp-specific IGA (ss-IGA) score of absence of disease (0) or very mild disease (1) at Week 16 among randomized participants with an ss-IGA score ≥ 3 at baseline.
7. The proportion of participants who achieve a static Physician's Global Assessment of Genitalia (sPGA-G) score of clear (0) or minimal (1) at Week 16 among randomized participants with an sPGA-G score ≥ 3 at baseline
8. The proportion of participants who achieve an intertriginous IGA (i-IGA) score of clear (0) or minimal (1) at Week 16 among randomized participants with an i-IGA score ≥ 3 at baseline
9. The proportion of participants who achieve a facial IGA (f-IGA) score of clear (0) or minimal (1) at Week 16 among randomized participants with an f-IGA score ≥ 3 at baseline
10. The change from baseline in Psoriasis Symptom and Sign Diary (PSSD) total symptom score at Week 16
11. The proportion of participants who achieve ≥ 4 -point reduction (improvement) from baseline in the Psoriasis Symptom and Sign Diary (PSSD) itch score at Week 16, among participants with baseline PSSD itch score ≥ 4 at baseline
12. The proportion of participants with PSSD individual symptom scale score = 0 at Week 16, among randomized participants with baseline PSSD > 0 at baseline. (Note: In this endpoint "individual symptom scale score = 0" is defined as "total symptom score = 0")

5.4.1.1. Definition of Endpoint(s)**5.4.1.1.1. Body or Scalp Surface Area Affected by Psoriasis**

The Body Surface Area (BSA) is a measurement of involved skin over the whole body. The overall BSA affected by psoriasis is estimated based on the participant's handprint (defined as the entire palmar surface of the hand including fingers). The surface area of the whole body is made up of approximately 100 "handprints" (as one "handprint" equates to approximately 1% of total body surface area).

The Scalp Surface Area (SSA) is a measurement of involved skin on the scalp. The adult SSA is around 520-705 cm², meaning that 1% SSA is about 5.2-7.1 cm². The thumbprint has an average surface area of about 5.5 cm² ± 1.3 cm². Hence, the thumb (in particular, the thumb projection) can be used as a tool for accurate measurement of 1% SSA). The overall SSA affected by psoriasis can thus be estimated based on the participant's thumb.

5.4.1.1.2. Psoriasis Area and Severity Index (PASI)

The PASI is a system used for assessing and grading the severity of psoriatic lesions and their response to therapy. In the PASI system, the body is divided into 4 regions: the head, trunk, upper extremities, and lower extremities. Each of these areas is assessed separately for erythema, induration, and scaling, which are each rated on a scale of 0 to 4. The PASI produces a numeric score that can range from 0 (no psoriasis) to 72. A higher score indicates more severe disease. Primary efficacy endpoint related to the PASI score is defined below:

PASI 90 Responder

Participants with ≥90% improvement in PASI from baseline will be considered PASI 90 responders.

PASI 100 Responder

Participants with a PASI score of 0 will be considered PASI 100 responders.

5.4.1.1.1. Investigator's Global Assessment (IGA) related endpoints**IGA cleared responder**

Participants who achieve an IGA score of cleared (0) will be considered IGA cleared responders.

5.4.1.1.2. Scalp-Specific Investigator's Global Assessment (ss-IGA)

The ss-IGA instrument is used to evaluate the disease severity of scalp psoriasis. The lesions are assessed in terms of the clinical signs of redness, thickness, and scaliness which are scored as: absence of disease (0), very mild disease (1), mild disease (2), moderate disease (3), or severe disease (4). The analysis for ss-IGA will be based on participants randomized at week 0 with baseline ss-IGA score ≥3. Efficacy endpoints related to the ss-IGA score is defined below:

ss-IGA absence of disease (0) or very mild disease (1) responder

Participants who achieve ss-IGA score of absence of disease (0) or mild disease (1) will be considered ss-IGA absence of disease (0) or very mild disease (1) responders.

ss-IGA absence of disease responder

Participants who achieve ss-IGA score of absence of disease (0) will be considered ss-IGA absence of disease responders.

5.4.1.1.3. Static Physician Global Assessment of Genitalia (sPGA-G)

The sPGA-G is used to evaluate the disease severity of genital psoriasis. Severity is determined by a combination of 3 plaque characteristics (erythema, elevation, and scale) based on the descriptions of each characteristic. The 6-point scale and associated severity categories are clear (0), minimal (1), mild (2), moderate (3), severe (4), and very severe (5).

sPGA-G clear (0) or minimal (1) responder

Participants who achieve sPGA-G score of clear (0) or minimal (1) will be considered sPGA-G clear or minimal responders.

5.4.1.1.4. Intertriginous Psoriasis Investigator's Global Assessment (i-IGA)

The IGA used for the full body assessment has been adapted with descriptions of disease features that are more consistent with intertriginous psoriasis presentation. The intertriginous areas affected to be scored include the axillary, sub-mammary, abdominal fold, inguinal, and intergluteal cleft/peri-anal region (distinct from genital/perineum involvement). The 5-point scale and associated severity categories are clear (0), minimal (1), mild (2), moderate (3), and severe (4). It should be noted that erythema may be the predominant feature and there may or may not be the presence of elevation or scaling. Therefore, scoring may be predominantly driven by the severity of erythema if it is the dominant presenting feature.

i-IGA clear (0) or minimal (1) responder

Participants who achieve i-IGA score of clear (0) or minimal (1) will be considered i-IGA clear or minimal responders.

5.4.1.1.5. Facial Psoriasis Investigator's Global Assessment (f-IGA)

The same IGA used for the full body assessment will be adapted for use, but only the face will be scored. The 5-point scale and associated severity categories are clear (0), minimal (1), mild (2), moderate (3), and severe (4). It should be noted that erythema, and to an extent, scaling, are the more prominent features of facial psoriasis and less often elevation. Therefore, scoring may be predominantly driven by the severity of erythema and scaling if these are the dominant presenting features.

f-IGA clear (0) or minimal (1) responder

Participants who achieve f-IGA score of clear (0) or minimal (1) will be considered f-IGA clear or minimal responders.

5.4.1.1.6. Psoriasis Symptom and Sign Diary (PSSD)

The PSSD includes PRO questionnaires designed to measure the severity of psoriasis symptoms and signs for the assessment of treatment benefits. The 7-day recall version asks the participant to answer the PRO questions thinking about the last 7 days. The PSSD is a self-administered PRO instrument and includes 11 items covering symptoms (itch, pain, stinging, burning and skin tightness) and patient observable signs (skin dryness, cracking, scaling, shedding or flaking, redness and bleeding) using 0 to 10 numerical rating scales for severity. Two subscores will be derived: the psoriasis symptom score and the psoriasis sign score. A higher score indicates more severe disease. For the entire study, from the screening visit through Week 48, participants will complete the 7-day recall version of the PSSD at study visits as indicated in the Schedule of Activities (See in the protocol).

The calculations of PSSD symptom, and sign scores are listed below:

Symptom Score (0-100)

- a. Symptom score includes itch (Q1), pain (Q11), stinging (Q10), burning (Q9) and skin tightness (Q4).
- b. Averaging items on the daily symptom scores when at least 3 items ($\geq 50\%$ of 5 items) on this scale are answered. Then, the average value is converted into 0-100 scoring such that Symptom score = average value x 10 with 0 representing the least severe and 100 the most severe.

Sign Score (0-100)

- a. Sign score includes skin dryness (Q2), cracking (Q3), scaling (Q5), shedding or flaking (Q6), redness (Q7) and bleeding (Q8).
- b. Averaging items on the sign scores when at least 3 items ($\geq 50\%$ of 6 items) on this scale are answered. Then, the average value is converted into 0-100 scoring such that Sign score = average value x 10 with 0 representing the least severe and 100 the most severe.

Seven daily symptom scores, and sign scores are averaged into a weekly score respectively (ie 7 days [from day -7 to -1] prior to a visit]. Four days out of 7 days (either consecutive or nonconsecutive) are necessary to derive a weekly score; otherwise, data are considered missing for that week.

Achieving \geq 4-point reduction (improvement) in PSSD itch score

Participant achieving at least a 4-point improvement from baseline in PSSD itch score.

PSSD symptom score of 0 a PSSD symptom score of 0

Participant achieving a PSSD symptom score of 0.

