### 1.3. Schedule of Activities (SoA)

Phase	Screening a	Placebo b				Active Treatment b								Follow-Up b,c		
Week		0	4	8	12	16	20	24	28	32	36	40	44 (last dose)	48 (Final Efficacy)	Early Term.	56 (Final Safety)
Study Procedures d																
Screening																
Informed Consent e	X															
ICF for optional pharmacogenomics e	X															
ICF for optional skin biomarker substudy e	X															
Medical History	X															
Demographics	X															
Inclusion/exclusion criteria	X	X														
Study Intervention Administration																
Randomization		X														
IP administration		CCI														
Efficacy Assessments																
BSA	X	X	X	X	X	X	X	X	X	X	X	X	X	X	X	
IGA	X	X	X	X	X	X	X	X	X	X	X	X	X	X	X	
PASI	X	X	X	X	X	X	X	X	X	X	X	X	X	X	X	
ss-IGA (scalp)	X	X	X	X	X	X	X	X	X	X	X	X	X	X	X	
f-IGA (facial)	X	X	X	X	X	X	X	X	X	X	X	X	X	X	X	
i-IGA (intertriginous)	X	X	X	X	X	X	X	X	X	X	X	X	X	X	X	
sPGA-G (genitals)	X	X	X	X	X	X	X	X	X	X	X	X	X	X	X	
pp-IGA (palmoplantar)	X	X	X	X	X	X	X	X	X	X	X	X	X	X	X	
NAPSI (all 10 fingernails)	X	X	X	X	X	X	X	X	X	X	X	X	X	X	X	
Clinical Photographs (half body + 1 special site or target lesion) f	X	X	X	X	X	X	X	X	X	X	X	X	X	X	X	
Patient-reported Outcomes																
PSSD (7-day version)		X	X	X	X	X	X	X	X	X	X	X	X	X	X	
DLQI		X	X	X	X	X	X	X	X	X	X	X	X	X	X	

Phase	Screening a	Placebo b				Active Treatment b								Follow-Up b,c		
Week		0	4	8	12	16	20	24	28	32	36	40	44 (last dose)	48 (Final Efficacy)	Early Term.	56 (Final Safety)
PEST (no history of PsA and PEST negative at screening) g	X	X		X		X		X		X		X		X	X	
PsAID-12 (rheumatologist confirmed history of PsA or positive PEST at screening) g		X		X		X		X		X		X		X	X	
PROMIS-29		X		X		X		X		X		X		X	X	
Safety Assessments																
Full Physical Examination (including skin)	X													X	X	X
Vital signs	X	X	X	X	X	X	X	X	X	X	X	X	X	X	X	X
12-lead ECG	X															
TB evaluation	X	X	X		X		X		X		X		X	X	X	X
Chest X-ray h	X															
C-SSRS i	X	X	X	X	X	X	X	X	X	X	X	X	X	X	X	X
Urine pregnancy test j		X	X	X	X	X	X	X	X	X	X	X	X	X	X	X
Height		X						X						X	X	X
Weight		X						X						X	X	X
Clinical Laboratory Assessments																
Serum pregnancy test j	X															
TB IGRA k	X															

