Hepatitis B and C serology l	X															
HIV Ab test	X															
Hematology	X	X	X		X	X		X		X				X	X	X
Chemistry	X	X	X		X	X		X		X				X	X	X
Lipid panel n		X						X						X	X	X
Hs-CRP		X	X			X		X		X				X	X	X
HbA1c		X						X						X	X	X

Phase	Screening a	Placebo b				Active Treatment b								Follow-Up b,c		
Week		0	4	8	12	16	20	24	28	32	36	40	44 (last dose)	48 (Final Efficacy)	Early Term.	56 (Final Safety)
Clinical Pharmacology and Biomarker Assessments p																
Serum guselkumab concentration		X	X			X				X				X	X	X
Anti-guselkumab antibodies		X	X			X				X				X	X	X
Serum biomarkers		X	X			X				X				X		
Optional Substudies e																
Skin biopsy p		X				X								X		
Tape stripping		X	X			X				X				X		
Whole blood (pharmacogenomics) q		X														
Ongoing Participant Review																
Concomitant therapy	X	X	X	X	X	X	X	X	X	X	X	X	X	X	X	X
Adverse events	X	X	X	X	X	X	X	X	X	X	X	X	X	X	X	X

a: The screening visit should occur within approximately 4 weeks before the Week 0 visit.

b: All post-baseline visits will have a visit window of  $\pm 7$  days counting from Week 0 as Day 1.

c: If a participant permanently discontinues study drug intervention prior to the Week 16 visit, they should be encouraged to return for all remaining study visits through Week 16, and the participant should also return for a final visit to perform assessments under the Week 56/final safety visit approximately 12 weeks after the last study intervention administration. If a participant permanently discontinues study drug at or after the Week 16 visit, they should complete the Week 48/final efficacy visit assessments at the time of discontinuation, or as soon as possible, and also return for a final safety visit to perform assessments under the Week 56/final safety visit approximately 12 weeks after the last study intervention administration.

d: All study procedures and evaluations should be completed before administration of study drug.

e: ICFs must be signed before the first study-related activity. The optional skin biopsy, tape stripping, and pharmacogenomics substudies will use separate ICFs.

f: Details may be found in the Photography Manual.

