#### **8.1.11.1. Psoriasis Symptom and Sign Diary (PSSD)**

The PSSD includes PRO questionnaires designed to measure the severity of psoriasis symptoms and signs for the assessment of treatment benefits. The PSSD is self-administered and includes 11 items covering symptoms (itch, pain, stinging, burning, and skin tightness) and patient-observable signs (skin dryness, cracking, scaling, shedding or flaking, redness, and bleeding) using 0 to 10 numerical rating scales for severity. Two subscores will be derived: the psoriasis symptom score and the psoriasis sign score. A higher score indicates more severe disease. Participants will complete the 7-day recall version of the PSSD (see Appendix 10.17) at study visits as indicated in the SoA.

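### SAP 5.4.1.1.6 derives the PSSD symptom and sign scores by a daily-diary rule that one 7-day-recall form per visit can never satisfy; taken literally, this blocks major secondary endpoints 10 and 12

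*SAP*

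**What the plan says.** **What is collected.** Protocol 8.1.11.1: "Participants will complete the 7-day recall version of the PSSD (see Appendix 10.17) at study visits as indicated in the SoA". The Schedule of Activities (Protocol 1.3) lists the 7-day version at Week 0, every 4 weeks to Week 48, and at early termination. The screening column is blank. Footnote i places participant questionnaires on the day of the visit. SAP 5.4.1.1.6 agrees on the instrument and timing: "participants will complete the 7-day recall version of the PSSD at study visits as indicated in the Schedule of Activities".

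**How it is scored.** SAP 5.4.1.1.6 has two steps.

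- Item step. The symptom score uses 5 items: "Averaging items on the daily symptom scores when at least 3 items" are answered, and the mean is multiplied by 10 to give 0 to 100. The sign score is built the same way from 6 items, but its bullet does not contain the word 'daily'.
- Weekly step. Seven daily symptom scores and seven daily sign scores, from day -7 to day -1 before the visit, are averaged into weekly scores. "Four days out of 7 days (either consecutive or nonconsecutive) are necessary to derive a weekly score"; with fewer, the week is missing.

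The itch responder definition in the same section is a 4-point improvement in the itch score. No daily or weekly derivation is attached to it.

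**The concern.** The weekly step belongs to a daily diary. This trial uses a form with a 7-day recall period, filled in once per visit, and neither document schedules daily entries. The step therefore asks for inputs that will not exist, and it says expressly what to do then: treat the score as missing.

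Two multiplicity-controlled endpoints depend on the symptom score. Endpoint 10 is the change in that score at Week 16. Endpoint 12 is defined in SAP 5.4.1 as a total symptom score of 0, among participants whose baseline score is above 0.

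The protocol offers no fallback. Sections 3 and 9.4.3 leave the data-handling rules for major secondary endpoints to the SAP. A programmer who scores the visit form directly, which is the sensible course, departs from the SAP on confirmatory endpoints. If the mismatch is noticed only after unblinding, the scoring choice is made post hoc.

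**Working it through.** **1. The plan's own figure.** SAP Table 5 gives power above 99% for the three PSSD endpoints with 200 and 100 participants, 2-sided alpha 0.05.

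- Endpoint 10 (changes -41.9, SD 24.61, and -3.0, SD 19.56): SE = √(19.56²/100 + 24.61²/200) = √(3.826 + 3.028) = 2.618. Then 38.9/2.618 = 14.86, so power is effectively 100%.
- Endpoint 11 (75.1% and 5.7%): pooled rate (5.7 + 150.2)/300 = 0.520. SE under the null is 0.0612 and under the alternative 0.0384. (0.694 - 1.96 × 0.0612)/0.0384 is about 15, so power is effectively 100%.
- Endpoint 12 (27.0% and 0.8%): pooled rate (0.8 + 54)/300 = 0.183. SE under the null is 0.0473 and under the alternative 0.0326. (0.262 - 1.96 × 0.0473)/0.0326 = 5.2, so power exceeds 99.9%.

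Table 5 reproduces. It takes the full 200 and 100 for endpoints 11 and 12, although both are restricted by baseline score and the eligible share is not given. Assuming shares of 50%, 30% and 20%, endpoint 12 has 99.8%, 94.0% and 77.3% power, and endpoint 11 stays above 99.9%. These figures presuppose that a score can be derived.

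**2. Forms available against forms required.** Scheduled visits are 28 days apart. "All post-baseline visits will have a visit window of" ±7 days, so consecutive visits stay at least 28 - 14 = 14 days apart, and no earlier scheduled form falls in the 7 days before a visit.

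| Count at each scheduled visit, Week 0 to Week 48 | Forms | Required |
|---|---|---|
| Days -7 to -1 | 0 | 4 |
| Last 7 days including the visit day | 1 | 4 |

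An extra early-termination form could raise the count by one at most. The requirement is not met at any visit.

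**3. Literal consequence by endpoint.**

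- Endpoint 10: SAP 5.4.1.3.2.2 does not impute missing scores, so the MMRM has no observed values. The only values would be the zero changes that Table 8 assigns after intercurrent events 1 or 2, and these would lack the baseline score that the model uses as a covariate.
- Endpoint 12: Table 9 restricts the analysis to a baseline symptom score above 0. With every baseline score missing, nobody qualifies. Non-responder imputation fills in a missing Week 16 response; it does not define who is in the population.
- Other endpoints: the same applies to item 16 and the symptom- and sign-score parts of item 17 in SAP 5.4.2.1, and to items 18, 23 and the corresponding parts of 24 in SAP 5.4.2.4. It applies to item 20 if the SAP 5.4.1 note equating that score with the total symptom score carries over.
- Endpoint 11 and the individual-item endpoints (items 14 and 15 in 5.4.2.1; 19, 21 and 22 in 5.4.2.4): the weekly step names only the symptom and sign scores, so these are outside it.
- Sequence: SAP 5.4.1.3.4.1 tests in the order of Table 2, where endpoints 10, 11 and 12 come last. If endpoint 10 yields no significant result, endpoint 11 cannot be claimed, even though its data can be scored. The primary endpoint and major secondary endpoints 1 to 9 are untouched.

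**The case against.** The strongest reply is that the section contradicts itself and has one natural resolution. Its opening and the protocol fix the instrument. Its item step already gives a complete 0 to 100 score from one form. The weekly step presupposes daily scores that the trial never generates, so it reads as text that does not fit. Total missingness would show at the first programming run, so a silent bias is unlikely.

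Much of this stands. A reader might infer that the PSSD endpoints cannot be analysed or that data are lost. The documents do not support that: the forms are collected and can be scored. A reader might also infer that every PSSD score is missing, or that itch endpoint 11 falls under the same rule. The wording covers the symptom and sign scores only, and itch is identified as item Q1. Nor is Table 5's power at issue.

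What does not stand is that the text can be left alone. It states a rule, and the rule gives the wrong result. Choosing the sensible reading is a decision about confirmatory endpoints that should be recorded before unblinding.

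SAP 5.4.1.1.6 also starts PSSD collection at screening, against Week 0 in the Schedule of Activities. This is minor: the sentence defers to the schedule, and baseline is the closest measurement at or before first dose.

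**Conclusion.** The concern holds as a scoring rule that is wrong as written. Read literally, it leaves 100% of the PSSD symptom and sign scores underivable: 0 forms in the window, or 1 if the visit day counts, against 4 required. That directly affects 2 of the 12 multiplicity-controlled secondary endpoints, 10 and 12, and the lower-tier endpoints built on the same two scores. Endpoint 11 is affected only through its place after endpoint 10.

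This rests on two premises: that no daily PSSD is collected, which both documents support, and that the weekly step is applied as stated. It is a correctable text error. It should be corrected because two confirmatory endpoints depend on it and the protocol (9.4) requires the SAP to be final before the first lock and unblinding.

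**What to change.** Amend SAP 5.4.1.1.6 before the Week 16 lock and unblinding:

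1. Delete the paragraph that averages seven daily scores and sets the 4-of-7-day minimum.
2. Delete 'daily' from the symptom-score bullet.
3. State that the visit score is the mean of the answered items on the single 7-day-recall form, multiplied by 10, with at least 3 items answered, and is missing otherwise.
4. State that the itch score for endpoint 11 is item Q1 of that form, on its 0 to 10 scale.
5. Align the start of collection with the Schedule of Activities (Week 0).

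The cost is SAP wording and one derivation specification. No data collection, sample size or test order changes.
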